# 2. STUDY PLAN

### 2.1 NAME AND INTENDED USE OF THE DEVICE

Device Classification & Generic Name: Class III; Total Disc Replacement

**Device Trade Name**: Simplify® Cervical Artificial Disc

Indication: Simplify® Cervical Artificial Disc is indicated for use in skeletally mature patients for reconstruction of the disc at one or two levels from C3-C7 following discectomy for intractable radiculopathy (arm pain and/or a neurological deficit) with or without neck pain, or myelopathy due to abnormality localized to the the disc space and manifested by at least one of the following conditions confirmed by radiographic imaging (e.g., X-rays, computed tomography (CT), magnetic resonance imaging (MRI)): herniated nucleus pulposus, spondylosis (defined by the presence of osteophytes), and/or visible loss of disc height as compared to adjacent levels. Patients receiving Simplify® Cervical Artificial Disc should have failed at least six weeks of non-operative treatment or demonstrated progressive signs or symptoms despite nonoperative treatment prior to implantation. Simplify® Cervical Artificial Disc is implanted via an open anterior approach.

#### 2.2 PURPOSE OF STUDY

This study is intended to demonstrate the 5-year long-term safety and efficacy of the Simplify® Cervical Artificial Disc ("Simplify Disc") in subjects enrolled in the non-randomized Simplify Disc IDE study. This study was conducted under IDE G140154.

#### 2.2.1 DESCRIPTION OF DEVICE

The Simplify Disc is a cervical artificial disc manufactured from PEEK endplates and a mobile, zirconia-toughened alumina ceramic core. The PEEK endplates have a plasma-sprayed titanium coating. The articulating surfaces on the endplates have a concave surface and the core has two convex surfaces.

Figure 1. Representative Image of Simplify Disc

For the Simplify Disc family, two core options (i.e., either small or large) are used for all assemblies. The articulating features of superior and inferior endplates are identical and congruent with the appropriate core. Superior and inferior endplates are available in three footprints, three thicknesses, and two lordosis angles. The superior endplates have a retention ring feature. All endplates are titanium coated on the bone interfacing surfaces, with two options available for coating thickness. All endplate components, regardless of configuration, have identical manufacturing process flow, including packaging and sterilization.

The Simplify Disc is designed to provide a theoretical maximum of  $\pm 12^{\circ}$  in any combination of flexion-extension and lateral bending, unlimited axial rotation, and 1-2 mm translation. This range is intended to permit the patient's anatomy to determine actual range of motion without imposing an artificial limit that may be restrictive to the patient's kinematic profile. The maximum range of motion *in vivo* will be dictated by the patient's anatomical boundaries or the device limits, whichever is smaller.

# 2.3 PROTOCOL STUDY CONDUCT

## 2.3.1 STUDY OBJECTIVE

The objective of this clinical study is to evaluate the 5 year long-term safety and effectiveness of the Simplify Disc compared to conventional anterior cervical discectomy and fusion ("ACDF") for treatment of intractable radiculopathy (arm pain and/or a neurological deficit) with or without neck pain or myelopathy due to a single-level abnormality localized to the level of the disc space at one level from C3 to C7 that is unresponsive to conservative management.

# 2.3.2 STUDY HYPOTHESIS

The study hypothesis is that in subjects with intractable radiculopathy (arm pain and/or a neurological deficit) with or without neck pain or myelopathy due to a single-level abnormality localized to the level of the disc space at one level from C3 to C7 that is unresponsive to conservative management, the Month 60 composite clinical success (CCS) rate of the Simplify Disc will be no worse than conventional ACDF. Individual success for Simplify Disc and the historical control ACDF is defined as follows:

- Improvement on the NDI of at least 15 percentage points compared to baseline (pre-op) in the Simplify Disc IDE study, and
- No device failures by Month 60, and
- No subsequent surgical procedure at the index level (including revision, removal, reoperation, or supplemental fixation) by Month 60.

# 2.3.3 STUDY DESCRIPTION

This is a prospective, multi-center post-approval study (PAS) evaluating subjects in the nonrandomized Simplify Disc IDE study compared to ACDF subjects in a non-concurrent historical control Kineflex®|C Disc study. The historical control population will only include the subjects who were selected using a PS model developed in the Simplify Disc IDE study and reviewed by FDA in the approved PMA to establish comparability between the study populations.

## 2.3.4 STUDY POPULATION

This will include up to 142 subjects eligible for study enrollment from fifteen (15) sites in the Simplify Disc IDE study who consent to long-term follow-up. Additionally, up to 13 training subjects from the Simplify Disc IDE study from thirteen (13) sites will be enrolled. Up to 106 historical ACDF control subjects will be included in the PAS population.

## 2.3.4.1 INCLUSION CRITERIA

All subjects enrolled in the Simplify Disc IDE study are considered for this long-term follow-up study.

## 2.3.4.2 EXCLUSION CRITERIA

Subjects meeting any of the following criteria will be excluded from the study:

- Subjects who were not implanted with the Simplify Disc during the IDE study
- Subjects who had a secondary surgical intervention at the index level during the IDE study
- Subjects who were withdrawn or withdrew consent to participate in the IDE study
- Subjects who do not consent to participate in long-term follow-up post-approval study

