# 2.3.6 STUDY PROCEDURES

## 2.3.6.1 INFORMED CONSENT

Only patients who sign Informed Consent for participation in PAS will be allowed to participate in this clinical study. Subjects who do not speak English must be provided a copy of an IRB approved consent in their native language, or (if the process is approved by the site's IRB) an IRB acceptable translator. The original signed consent will be retained in each subject's study file.

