#### 2.3.7.3 DESIGN OF THE OBSERVATIONAL STUDY

One hundred sixty-six (166) subjects were enrolled in the Simplify Disc IDE population. Of these, 16 Simplify Disc subjects were training subjects. The historical ACDF control population included 133 subjects. The 283 available subjects (150 Simplify Disc (excluding training subjects) and 133 historical ACDF control) were assessed via the Propensity Score (PS) sub-classification process. After applying an established heuristic for 3 iterations (6 models), a total of 150 Simplify Disc and 117 historical ACDF control subjects were retained in the final PS designed sample. Analysis of subject demographic and baseline data showed no meaningful differences between the treatment groups. The PS-selected population and PS sub classes defined in the IDE study will be utilized for the purposes of this study. Per the exclusion criteria, additional subjects are not enrolled into the PAS due to reasons that preclude long-term Simplify Disc data collection (e.g., SSI).

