#### 2.3.7.7 ADDRESSING MISSING PRIMARY OUTCOME DATA

Because of the availability of subject level data in controls that correspond to the subject level data to be collected in the prospective study, missing data will be addressed in the same fashion to how missing data would have been addressed in a randomized clinical trial. Multiple imputation will be used to impute missing final NDI in patients otherwise evaluable for primary CCS. For each of 20 imputed data sets, the primary PS stratified device group difference will be made resulting in a standard error for each. The final device group difference will be the average of the multiple imputed datasets and its standard error will account for both within (usual) and between imputation error.

In addition to multiple imputation, sensitivity analysis will be provided based on tipping point analyses. These are analyses in which all possible combinations of successes and failures are assumed for patients missing primary CCS and the fraction of scenarios in which the statistical conclusion changes is summarized. Best case and worst case, all missing success, and all missing failures scenarios will also be summarized.

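### Declining the post-approval study removes eligible Simplify subjects from the population, while controls not seen after Month 24 stay in it as missing

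*Combined protocol and SAP*

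**What the plan says.** Section 2.3.4 limits the Simplify group to up to 142 "subjects eligible for study enrollment from fifteen (15) sites in the Simplify Disc IDE study who consent to long-term follow-up". Section 2.3.4.2 lists as an exclusion "Subjects who do not consent to participate in long-term follow-up post-approval study", and 2.3.6.1 repeats the condition: "Only patients who sign Informed Consent for participation in PAS will be allowed to participate in this clinical study". For the comparator, 2.3.4 says only this: "Up to 106 historical ACDF control subjects will be included in the PAS population". No consent step is described for controls.

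Section 2.3.7.3 reports that "a total of 150 Simplify Disc and 117 historical ACDF control subjects were retained in the final PS designed sample" and continues: "The PS-selected population and PS sub classes defined in the IDE study will be utilized for the purposes of this study". It then says that the exclusion criteria keep further subjects out of the post-approval study (PAS). Section 2.3.7.5 describes 142 and 106 as the subjects in each arm who were neither terminal failures nor lost by Month 24. It expects 121 and 64 of them to be available at year 5.

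Section 2.3.7.7 says missing data will be handled as they would be in a randomised trial. It plans multiple imputation of the final NDI where the subject is otherwise evaluable, and a tipping-point analysis over patients missing the composite outcome. It adds: "Best case and worst case, all missing success, and all missing failures scenarios will also be summarized". Section 2.3.7.6 refers to a primary analysis set, which no section defines.

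**The concern.** Take one Simplify subject and one control, each unrevised and followed to Month 24, and neither seen again. The control is among the 106 and has a missing Month 60 outcome. If the Simplify subject was not seen again because of declining the PAS, that subject meets an exclusion criterion and is outside the population.

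Consent to long-term follow-up is given after surgery, by someone who knows how the treated level has done so far. As a membership rule, it selects one arm on a post-treatment variable. The propensity-score subclasses were built on baseline data and cannot correct for that. In a randomised trial, which 2.3.7.7 takes as its model, a treated subject who does not come back is missing data and not ineligible.

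The consequence is that the sensitivity analyses meant to expose the effect of non-return cannot see these subjects. Section 2.5.3 asks for reasons for non-participation to be documented, but that does not put anyone back in the denominator.

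**Working it through.** **Inputs.** From 2.3.7.5: 142 and 106 subjects at Month 24, 121 and 64 available at year 5, success rates of 65% and 50%, one-sided alpha 0.05. From 2.3.7.2: margin 0.10. The number of decliners, x, is not in the documents and is assumed to be 5 to 21. All results are unadjusted for propensity score.

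**The plan's own figures.** 142 × 0.85 = 120.7 (121) and 106 × 0.60 = 63.6 (64). The expected losses are therefore 142 - 121 = 21 and 106 - 64 = 42. For power, SE = √(0.65×0.35/121 + 0.50×0.50/64) = 0.0761, and Φ((0.15 + 0.10)/0.0761 - 1.645) = 95.0%. This is within rounding and method differences of the stated 96% (95.6% with 70% of the completer rates, unrounded).

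**Where the asymmetry begins.** Before Month 24 both arms shrink in the same way: 150 - 142 = 8 Simplify and 117 - 106 = 11 control subjects leave. The one-arm rule acts only after that.

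**Scenarios.** Observed successes are 0.65 × 121 ≈ 79 and 0.50 × 64 = 32. If decliners are kept, Simplify has n = 142 with 21 missing. If they are removed, n = 142 - x with 21 - x missing. The control arm has n = 106 with 42 missing throughout, so its successes are 32 (missing = failure) or 32 + 42 = 74 (missing = success). The lower bound is d - 1.645 × √(p₁(1-p₁)/n₁ + p₂(1-p₂)/n₂).

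Difference in percentage points, with the one-sided 95% lower bound in brackets:

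| Scenario | Kept | Removed, x = 5 | Removed, x = 21 |
|---|---|---|---|
| All missing fail | +25.4 (+15.4) | +27.5 (+17.4) | +35.1 (+24.9) |
| Worst case for Simplify | -14.2 (-24.2) | -12.1 (-22.2) | -4.5 (-14.7) |
| All missing succeed | +0.6 (-9.1) | -0.5 (-10.3) | -4.5 (-14.7) |
| Best case for Simplify | +40.2 (+30.6) | +39.2 (+29.4) | +35.1 (+24.9) |

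For example, all-failure kept is 79/142 - 32/106 = 0.556 - 0.302 = +25.4. With all 21 removed it is 79/121 - 32/106 = 0.653 - 0.302 = +35.1.

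Against a bound of -10, the worst case fails either way, and the all-failure and best cases pass either way. The all-success case passes if decliners are kept and fails if they are removed. Over the full tipping-point grid, the share of cells meeting non-inferiority is 772/946 = 81.6% if kept. If removed it is 605/731 = 82.8% (x = 5) to 37/43 = 86.0% (x = 21).

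**Primary estimate.** The overstatement of the Simplify rate equals the share declining times the success gap between those who enrol and those who decline. Both factors are assumptions. A 10% share with a 10-point gap gives 1 point; 15% with a 20-point gap gives 3 points. The 15% share is close to the case where all expected losses are decliners (21/142 = 14.8%). At 79/121 against 32/64 the difference is 15.3 points, SE 7.6, lower bound +2.8. With the Simplify rate 3 points lower, the difference is 12.3, SE about 7.6, lower bound about -0.3.

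**The case against.** The strongest reply is that 2.3.4, 2.3.4.2 and 2.3.6.1 govern who may be enrolled and give new data, not who is analysed. Section 2.3.7.3 says the IDE propensity-score population will be used, and 2.3.7.5 applies its 85% to the full 142, which could mean that decliners count as unavailable within that base. This stands in part: removal from the analysis is an inference. It is the natural one, because 2.3.7.3 itself goes on to apply the exclusion criteria and no definition of the analysis set brings these subjects back. If the sponsor intends the other reading, the plan needs to say so.

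Second, imputation is limited to subjects otherwise evaluable. A control lost with unknown surgery or device status might therefore not be imputed either. That also stands. The contrast between arms is clearest in the tipping-point and extreme-case analyses, which do not decide study success. Whether controls passed a consent step for later follow-up in their own study cannot be seen here.

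Three stronger readings are tempting, and the documents do not support them.

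- A reader might infer that every control loss is retained. The fall from 117 to 106 shows otherwise.
- The worst-case differences of -14.2 and -4.5 lie on opposite sides of -10, so a reader might infer that exclusion rescues non-inferiority. Those are point estimates. The criterion in 2.3.7.2 is a one-sided 0.05 test, and by lower bounds the worst case fails both ways.
- A reader might add the exclusion of "Subjects who were withdrawn or withdrew consent to participate in the IDE study" as further one-arm selection. Losses by Month 24 leave both bases, so it adds little.

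**Conclusion.** The concern holds for losses after Month 24. A consent decision made after treatment removes Simplify subjects from the population, controls face no counterpart described in the plan, and the sensitivity analyses in 2.3.7.7 cannot reveal the effect. If 5 to 21 of the 21 expected losses are decliners, their removal shifts the all-failure and worst-case differences by 2.0 to 9.7 points towards Simplify and the all-success difference by 1.1 to 5.1 points against it. Only the all-success scenario changes its non-inferiority conclusion.

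A reader might infer that the plan is biased in favour of the device. The documents do not establish that. The direction in the primary estimate depends on whether decliners do worse than those who enrol, and nothing in the documents says so. If they do, a 3-point overstatement would not threaten non-inferiority at the planning rates, since the lower bound of about -0.3 is far from -10. It could decide the superiority test in 2.3.7.6, where the bound moves from about +2.8 to just below zero. The 96% power figure is unaffected, because it counts only subjects available at year 5. The change should be made: it is inexpensive and settles which denominator is used.

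**What to change.** In 2.3.4.2 and 2.3.7.7, keep consent as a condition for collecting new PAS data, but not for membership of the primary analysis set.

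- Define the primary analysis set as the propensity-score-selected subjects in each arm who were neither terminal failures nor lost by Month 24, by the same rule in both arms.
- Count eligible Simplify decliners as missing the Month 60 composite, on the same terms as controls lost after Month 24. State that imputation covers both, using baseline data and study data through Month 24.
- Include decliners in the tipping-point, best-case, worst-case, all-success and all-failure analyses.
- Report the consented-only set as a sensitivity analysis, with the number of decliners.
- Do not restore IDE withdrawals in the Simplify arm alone. That would create a new imbalance, because controls lost by Month 24 stay outside the 106.

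How index-level surgery during the IDE is scored is a separate question that this change does not settle. The sponsor should confirm that the IDE consent terms, which are not in these documents, allow this use of the Month 24 data.

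The cost is wording and some extra imputation work, with no new visits or subjects. The downside is more reported missing data in the Simplify arm and a somewhat wider estimate.

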# 2.3.5 STUDY DESIGN

### 2.3.5.1 OVERALL STUDY DESIGN

This is a prospective, multi-center post-approval study to evaluate the 5-year long term safety and effectiveness of the Simplify Disc. The historical control population will only include the fusion subjects who were selected using a PS model developed in the Simplify Disc IDE study and approved PMA. The Simplify Disc data from the training subjects will be summarized separately and not used in the primary comparison to control. Study subjects will be evaluated annually ( $\pm$  2 months) for components of the primary endpoint, secondary study endpoints and safety up through 5-year post-implantation. Primary study success will be evaluated at the 5-year timepoint.

# 2.3.6 STUDY PROCEDURES

## 2.3.6.1 INFORMED CONSENT

Only patients who sign Informed Consent for participation in PAS will be allowed to participate in this clinical study. Subjects who do not speak English must be provided a copy of an IRB approved consent in their native language, or (if the process is approved by the site's IRB) an IRB acceptable translator. The original signed consent will be retained in each subject's study file.

## 2.3.6.2 STUDY EVALUATIONS, PROCEDURES AND ASSESSMENTS

Follow-up evaluations annually at Month 36, Month 48, and Month 60 will include:

- AP and lateral X-rays (plain films);
- Flexion-extension X-rays (used to determine range of motion);
- Lateral bending films (Simplify Disc only);
- Radiographic core lab evaluations;
- Dysphagia Handicap Index (Simplify Disc only);
- NDI assessment;
- SF-12v2 Health Survey (Simplify Disc only);
- VAS pain assessments (neck and arm; neck, left arm and right arm (Simplify Disc only));
- Neurologic evaluation;
- Study related medication status (Simplify Disc Only);
- Work status;
- Treatment satisfaction assessment and
- Adverse events as defined by Section 2.3.8 of this protocol.
- •

Neurologic status will be evaluated by a qualified evaluator, who may be an MD, DO, an RN or a PA. The neurologic evaluation will include a motor and sensory assessment, reflex responses and the determination of the presence or absence of dysphagia, dysphonia, clumsiness, foot drop, atrophy, cramping, muscle spasms, numbness and gait abnormality.

Muscle strength will be graded for the deltoid (C5), biceps (C6), and triceps (C7) according to a 6point scale where 0 = no movement, 1 = trace of muscle contraction; 2 = active movement without gravity; 3 = active movement against gravity; 4 = active movement against gravity/resistance; and 5 =normal response.

Study related medication status will include only medications taken or administered for the following

- Pain (any type);
- Inflammation (any type);

- Muscle relaxation;
- Numbness &/or tingling;
- Hormonal replacement therapy and
- Other medications related to or given for the subject's spinal condition.

All radiographic endpoints will be evaluated independently by one core laboratory.

## 2.3.6.2.1 Radiographic Assessments

The following radiographic assessments will be made by two independent musculoskeletal radiologists at the core lab. A third independent radiographic reviewer will adjudicate in instances of disagreement. The radiographic assessments will include:

- Angular Motion;
- Change in Angular Motion;
- Translational Motion;
- Change in Translational Motion;
- Global Range of Motion;
- Change in Global Range of Motion;
- Disc Height;
- Change in Disc Height;
- Disc Angle;
- Change in Disc Angle;
- Spondylolisthesis;
- Change in Spondylolisthesis;
- Bridging Bone;
- Fusion Status;
- Device Condition;
- Device Subsidence;
- Device Migration;
- Device Protrusion;
- Radiolucency;
- Heterotopic Ossification;

- Osteophyte Formation;
- Endplate Sclerosis;
- Adjacent Level Disc Degeneration;
- Change in ALDD and;
- Additional Observations.

#### 2.3.6.2.3 Study Completion, Termination or Loss to Follow-up

Simpliy Disc subjects are expected to remain in the study until the 60 months post implantation assessment. The study completion/ termination evaluation will be made at the 60 months assessment, or at earlier time point if the subject withdraws or is withdrawn from the study.

Subjects may be withdrawn from a clinical study early due to withdrawal of Informed Consent, loss to follow-up, or Investigator medical decision. Any premature termination from the study will be documented, including the primary reason for withdrawal. In the event of a secondary index surgery requiring removal of a spinal system, every effort will be made to retrieve the explanted device for analysis. The instructions for the surgical technique for device removal of the Simplify Disc are included in the Study Manuals. Any subjects with a device removal of the Simplify Disc or who have any other secondary index surgery will be discontinued from the study after the next follow-up study visit.

# 2.3.7 STATISTICAL CONSIDERATIONS

#### 2.3.7.1 PRIMARY ENDPOINT

The study hypothesis is that in subjects with intractable radiculopathy (arm pain and/or a neurological deficit) with or without neck pain or myelopathy due to a single-level abnormality localized to the level of the disc space at one level from C3 to C7 that is unresponsive to conservative management or have the presence of progressive symptoms, the Month 60 composite clinical success (CCS) rate of the Simplify Disc will be no worse than conventional ACDF when success of ACDF is evaluated at Month 60. Individual success for Simplify Disc and the historical control ACDF is defined as follows:

- Improvement on the NDI of at least 15 percentage points compared to baseline in the Simplify Disc IDE study, and
- No device failures by Month 60, and
- No subsequent surgical procedure at the index level (including revision, removal, reoperation, or supplemental fixation) by Month 60.

Device failure is defined as breakage, migration, or mechanical failure of the components as defined in the Radiographic Evaluation Protocol. Failure of the allograft will not be counted as device failure in the historical ACDF control group.

Per FDA Guidance for the Preparation of IDEs for Spinal Systems, the following definitions apply for the PAS:

- Reoperation any surgical procedure at the index level that *does not involve* modification, addition or removal of any components of the device" in the postoperative or follow-up period.
- Revision any procedure in the postoperative or follow-up period that adjusts modifies or removes part of the original implant configuration *with or without* replacement of a component – may include adjusting the position of the original configuration in the postoperative or follow-up period.
- Removal a procedure where the entire device is removed with or without replacement of the device in the postoperative or follow-up period.

• Supplemental fixation – a procedure in which additional instrumentation not under study is implanted (e.g., supplemental placement of a rod/ screw system).

